Subjects will be recruited from three different sites and among the licensed health care provider's test site's pool of patients who are currently being treated for, or who are seeking treatment for Lateral Epicondylitis, or from patients who respond to the following recruitment materials, if needed.

Flyer

WANTED

ADULTS WITH LATERAL EPICONDYLITIS, ONGOING
FOR ONE MONTH, FOR A CLINICAL STUDY
OF THE EFFECTS OF LOW-LEVEL LASER LIGHT ON REDUCING LATERAL
EPICONDYLITIS.

**THIS STUDY INVOLVES SIX LASER LIGHT PROCEDURES, TWO TIMES A WEEKS FOR
THREE WEEKS WITH THE MULTI RADIANCE MEDICAL® MR5® LASER AT THE TEST
SITE.**

THERE IS THREE VISITS PRIOR TO LASER LIGHT PROCEDURES WITH ONE MORE
VISIT TO THE TEST SITE
ONE MONTH AFTER THE LAST LASER LIGHT PROCEDURE.

YOU WILL RECEIVE \$450 IF YOU FINISH THE STUDY.

FOR MORE INFORMATION PLEASE CONTACT:

<PI name>
<test site name & location>
<phone # and/or e-mail>

Newspaper Ad

**Lateral Epicondylitis
Research Study**

This study is to see if the Multi Radiance Medical® MR5® LASER, a non-invasive, investigational device that uses low-level laser light, can help to relieve symptoms of Lateral Epicondylitis pain longer than one month in duration.

The study involves ten visits to a test site and recording some information at home.

You will receive \$450 if you finish the study. Please contact
<PI name> at
<test site name & location> at
<phone and/or e-mail> for details.

Compensation

A subject will be paid a stipend of \$450.00 USD for their participation in the study upon completion. Subjects will not be charged for the cost of the study procedures administered with the Multi Radiance Medical® MR5® Prototype Device for the cost of any other directly related evaluations or measurements that occur as part of his or her participation in the study.

Sample size

There will be 60 subjects evaluated for eligibility in this clinical study:

- 30 subjects in the active procedure group
- 30 subjects in the control procedure group (Placebo)

Rationale for sample size

Based on the following parameters established for the purposes of assessing efficacy of the Multi Radiance Medical MR5 Prototype Device in this clinical study using the Fischer's Exact test to assess the primary endpoint.

- Individual subject success criteria is defined as a 30% or greater reduction in self-reported Degree of Pain rating on the 0-100 VAS from baseline to study endpoint evaluation.

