- Overall study success criteria of at least a 30% difference between the test device group and the placebo group, comparing the proportion of individual successes in each group.
- It is anticipated that about 50% of subjects in the test device group and about 20% of subjects in the placebo group will meet the individual success criteria, and
- Intended application of a two-tailed test with an alpha value of 0.05 and Power of 0.8

- the sample size of 25 available subjects per group (test group and the control group, separately) has been determined using the following reference calculator: *Hypothesis Testing: Categorical Data - Estimation of Sample Size and Power for Comparing Two Binomial Proportions* in Bernard Rosner's *Fundamentals of Biostatistics*.

For the purposes of sample size calculation, a subject loss-to-follow-up of 20% is anticipated.

Therefore, a minimum starting sample size of 30 evaluable subjects in each group is needed to ensure that a sufficient number remains at the end of the trial (25 subjects per group) for any significant differences found between groups to be considered statistically valid and representative of the general population being sampled. This results in a total of 60 subjects being enrolled in this study across both study procedure groups.

RANDOMIZATION

Subject allocation to procedure group will be via variable block randomization with varying block sizes of two and four used at random to minimize the likelihood of predicting the next procedure group assignment. In addition, randomization will be stratified by Fitzpatrick Skin Type grouping

Randomization will be attained using computer generation sequence methodology, ensuring that the randomization methodology and the generated allocation sequence is concealed from the investigator and subjects.

Concealment will be insured as follows:

- Each computer-generated randomization sequence is unique and will therefore not be able to be replicated.
- Randomization will occur to either 'Test Group A' or 'B' rather than to a tests or placebo group, and only the study Sponsor will know which assignment corresponds to the active devices and which corresponds to the fake device. The Sponsor will not reveal this information to any source (investigators, subjects, or study Monitor) until the final study data analysis is complete.

TRIPLE BLIND DESIGN

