Daily throughout the one-week post-procedure administration phase, the subject will continue at home to:

- maintain application of his or her individualized pain management regimen, as during the two-week stabilization phase and the three-week procedure and phase, and
- complete the Subject Daily Diary, as applicable

ONE MONTH POST-PROCEDURE ADMINISTRATION PHASE (TEST SITE VISIT)

- Degree of Pain Rating: This time will be within the same one-hour time-frame as the prior post-procedure administration phase VAS ratings were recorded, 1 month after the final procedure administration; e.g., if the prior 3 post-procedure administration VAS recordings were made between 1:30 p.m. and 2:30 p.m. on each of the three days, then the 1 week post-procedure VAS recording will also be made between 1:30 p.m. and 2:30 p.m. The exact time the VAS rating is recorded will be noted.
- PRTEE, Grip Strength and TNFa measurements will be noted.
- Subject Satisfaction with Overall Outcome Rating
- Perceived Group Assignment
- Investigator Adverse Events Evaluation

ADVERSE EVENTS

At each evaluation and measurement point throughout the clinical study, and at any other time throughout the duration of the clinical trial that is necessary, any and all potential adverse events reported by a subject or observed by an investigator will be recorded on the case report form, and subsequently evaluated by the investigator for its relation to the study procedure and whether or not any corrective action needs to be taken. All potential adverse events recorded will be appropriately reported to the governing IRB, as applicable.

It is unlikely and not expected that any adverse events will result from implementation of this clinical study protocol. Prior clinical trials using low level laser light have not typically yielded any adverse events or reactions. However, potential adverse events that may feasibly occur from application of the Multi Radiance Medical® MR5® Prototype Device include, but are not necessarily limited to; skin irritation, discoloring, rash, indentations and infection.

PRIVACY AND CONFIDENTIALITY

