FITZPATRICK SKIN TYPE CLASSIFICATION SCALE: The Fitzpatrick Skin Type Classification Scale is a numerical classification schema for human skin color developed in 1975 by Harvard Medical School dermatologist, [name], PhD. The scale classifies a person's complexion and their tolerance of sunlight.

The Fitzpatrick Classification Scale classifies skin type from I through VI according to the applicable criteria contained in the chart below.

Skin Type	Skin Color	Characteristics
I	White; very fair; red or blond hair; blue eyes; freckles	Always burns, never tans
II	White; fair; red or blond hair; blue, hazel, or green eyes	Usually burns, tans with difficulty
III	Cream white; fair with any eye or hair color; very common	Sometimes mild burn, gradually tans
IV	Brown; typical Mediterranean Caucasian skin	Rarely burns, tans with ease
V	Dark Brown; mid-eastern skin types	Very rarely burns, tans very easily
VI	Black	Never burns, tans very easily

POOLABILITY EVALUATION

The primary efficacy outcome is a binary variable, with success defined as a 30% or greater reduction in self-reported Degree of Pain rating on the 0-100 VAS from baseline to study endpoint evaluation. Poolability analysis for this primary binary outcome will be via the Breslow-Day test for homogeneity of odds ratios.

Furthermore, poolability analysis will also be conducted for the continuous outcome of mean change from baseline to study endpoint in self-reported Degree of Pain ratings on the 0-100 VAS through a treatment-by-subgroup interaction term applying a logistic regression model that also includes the main effect terms of all treatment groups.

SAFETY ANALYSES

Safety analyses will be based on all subjects who were randomized to the test or to the placebo procedure group. Safety will be assessed by evaluating and comparing frequency and incidence of observed and/or reported adverse events between test and placebo procedure groups. A chi-square test with a continuity correction will be performed to compare the percentage of subjects who had adverse events between test and placebo group subjects.

CASE REPORT FORMS

The case report forms that will be used to collect the data from each subject in this clinical study can be found in **Appendix E**.

REFERENCES

ⁱ Bocock MG, Collier JM, McNair PJ, Simmonds M, Larmer PJ, Armstrong B. A framework for the classification and diagnosis of work-related upper extremity conditions: systematic review. *Semin Arthritis Rheum*. 2009;38:296-311.

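### The only inferential safety method is a continuity-corrected chi-square test that has low power at 30 per arm and is undefined with no events; no confidence interval is planned

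*Combined protocol and SAP*

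**What the plan says.** The SAFETY ANALYSES section defines the population ("Safety analyses will be based on all subjects who were randomized to the test or to the placebo procedure group") and the general aim: "Safety will be assessed by evaluating and comparing frequency and incidence of observed and/or reported adverse events between test and placebo procedure groups". It then names one inferential procedure: "A chi-square test with a continuity correction will be performed to compare the percentage of subjects who had adverse events between test and placebo" subjects. It gives no confidence interval, upper bound, safety hypothesis, significance level or power.

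The ADVERSE EVENTS section has every potential event recorded and judged by the investigator for its relation to the procedure. It also states the expectation: "It is unlikely and not expected that any adverse events will result from implementation of this clinical study protocol".

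The Sample size section plans "30 subjects in the active procedure group" and the same number on placebo. The sizing rationale concerns the pain-response endpoint only.

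**The concern.** A test of no difference answers a narrow question, and with 60 subjects and few expected events it answers it poorly. A non-significant p-value cannot separate a device that causes no events from one that causes them in, say, one subject in ten. The test is also a poor match for the protocol's own expectation. With no events it has no value, and with fewer than 10 events over two equal arms the expected event count per arm is below 5, where the chi-square approximation is unreliable.

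The sponsor intends to use the results in a De Novo submission (PROPOSED INDICATIONS FOR USE). A reader of that submission will want to know how high the event rate on the device could be. The planned analysis does not say. An interval would.

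**Working it through.** **Inputs.** 30 per arm (Sample size), which is also the planned safety set because all randomized subjects count. The plan gives no safety level, so I take two-sided 5%, by analogy with the efficacy sizing ("Intended application of a two-tailed test with an alpha value of 0.05 and Power of 0.8"). It gives no adverse-event rates, so those below are assumptions shown over a range. It states no safety power or detectable difference, so there is no figure to reproduce.

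**Step 1: where significance starts.** With *a* of 30 device subjects and *b* of 30 placebo subjects having events, and *m* = *a* + *b*, the corrected statistic is

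60 × (|*a*(30 − *b*) − *b*(30 − *a*)| − 30)² / (30 × 30 × *m* × (60 − *m*)).

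- 5 v 0: 60 × (150 − 30)² / (900 × 5 × 55) = 864,000 / 247,500 = 3.49, p = 0.062.
- 6 v 0: 60 × (180 − 30)² / (900 × 6 × 54) = 1,350,000 / 291,600 = 4.63, p = 0.031.

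Significance therefore needs at least 6 v 0. The same calculation gives 8 v 1, 9 v 2 and 11 v 3 as the next thresholds.

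**Step 2: no events.** With *m* = 0 the denominator is zero. The corrected statistic has no value.

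**Step 3: chance of missing an excess.** If the placebo rate is 0%, the test misses whenever the device arm has five or fewer subjects with events. For a 10% device rate this is P(X ≤ 5), X binomial (30, 0.10), = 0.927. For non-zero placebo rates I summed the binomial probabilities over all tables and counted only rejections towards harm.

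| Placebo rate | Device rate | Missed |
|---|---|---|
| 0% | 5% | 99.7% |
| 0% | 10% | 93% |
| 0% | 15% | 71% |
| 0% | 20% | 43% |
| 0% | 25% | 20% |
| 0% | 30% | 8% |
| 5% | 15% | 91% |
| 5% | 20% | 76% |
| 5% | 30% | 37% |
| 5% | 40% | 11% |
| 10% | 30% | 63% |

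Power of 80% needs a device rate of about 25%, 36% or 44% when the placebo rate is 0%, 5% or 10%.

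**Step 4: true size.** With equal rates in both arms, the probability of any rejection is about 0.15% at a 5% rate and 0.9% at a 10% rate, against the nominal 5%.

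**Step 5: alternatives.** Over all tables at 30 per arm, Fisher's exact test at 5% rejects exactly the same tables as the planned test (5 v 0 gives 0.052, 6 v 0 gives 0.024). An unconditional exact test takes the probability of a result at least as extreme and maximises it over the common event rate. For 5 v 0 this gives about 0.027 (Boschloo) and 0.023 (Barnard), both below 0.05.

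**Step 6: what an interval would show.** With 0/30 the Clopper-Pearson two-sided 95% upper limit is 1 − 0.025^(1/30) = 11.6%. It is 17.2% for 1/30 and 26.5% for 3/30. For 5/30 v 0/30 a Newcombe 95% interval for the difference, used here as an approximation, runs from about +2 to +34 points, although the planned test is not significant.

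**The case against.** Four points can be made for the plan.

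- **The test is not blind to harm.** A reader might infer that a non-significant result is close to guaranteed even for a clearly harmful device. The numbers do not support that: 20% v 0% is detected more often than not, 25% v 0% is missed 20% of the time and 30% v 0% only 8%. Near-certain non-significance is confined to excesses of about 10 points or less.
- **The test is not the whole safety assessment.** Adverse events are also compared descriptively, and the investigator reviews each one. This stands, but neither element quantifies the rates that the data exclude.
- **The plan never equates non-significance with safety.** It sets no safety hypothesis or success rule, and low power for adverse events is usual in a trial sized for efficacy. This stands too. It also means that the absence of a margin is not a defect. Reading non-significance as reassurance is a risk that the plan leaves open, not an error that it makes.
- **The continuity correction is not the cause relative to Fisher's test.** The two give identical decisions at 30 per arm, so a switch to Fisher's test would gain nothing except a defined result with no events. The low power comes from the sample size and from the conservatism that both tests share.

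A reader with the counts could also compute intervals afterwards. That is true, but it leaves the method, and the weight given to it, to be chosen after the data are seen.

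**Conclusion.** The point holds in a limited form. The one inferential safety method has less than 80% power for excesses below about 25 points over a placebo rate of zero, and very little (about 7%) at 10 points. It is far below its nominal size when events are sparse, and it gives no result in the no-event case that the protocol expects. No planned interval fills the gap. The documents do not support the stronger claims that the test would pass almost any harmful device or that the sponsor will treat a non-significant result as proof of safety.

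The figures assume 30 per arm, a two-sided 5% level and the event rates shown; the last two are not in the documents. This is a worthwhile, inexpensive improvement to analysis and reporting. It does not touch the primary efficacy result.

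**What to change.** In SAFETY ANALYSES, replace the chi-square sentence with wording such as:

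> *For any adverse event and for any device-related adverse event, the number and percentage of subjects will be reported per group, with an exact (Clopper-Pearson) 95% confidence interval for the test-group rate and an exact unconditional 95% confidence interval for the test-minus-placebo difference. Safety conclusions will rest on these intervals. A non-significant comparison will not be taken as evidence of safety.*

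If a p-value is kept, specify an exact unconditional test (Boschloo or Barnard), state its level and label it descriptive. No margin is needed.

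The change costs a few sentences and a few lines of code. It needs no further subjects, visits or data, because relation to the procedure is already recorded. The downside for the sponsor is a less favourable safety statement: no events in 30 would be reported as compatible with a rate up to about 12%.

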For a group using the questionnaire, mean PRTEE score reductions of at least 11 points - or an improvement of 37% on the mean baseline score - is necessary to consider that a substantial improvement has taken place. Using a less stringent criterion, falls of 7 points or 22% of the baseline score can be interpreted as indicating a limited but meaningful improvement.^{xcviii}

Grip Strength Test

The grip strength will be measured using a digital grip dynamometer type Jamar® Plus Digital Hand Dynamometer (Patterson Medical, Warrenville, IL, USA). The grip dynamometer will be placed on the second knuckle of the finger to measure the grip strength between the thumb and the other fingers, and the subject will grip the grip dynamometer for five seconds within the range where no pain will be felt, with both arms naturally lowered while ensuring that the grip dynamometer will not be shaken or put into contact with the body. This measurement will be conducted three times and the average value will be used (Lee et al. 2018).

TNF- α Marker - Blood Collection

Blood samples (5 ml) will be collected by puncture of the antecubital vein. The collections will be performed by a qualified professional who will use sterile gloves, disposable syringes and needles. The collected material will be placed in centrifuge tubes. Fifteen minutes after obtaining the blood sample, it will be centrifuged and the supernatant (serum) stored at -80°C for further analysis. An analysis of the concentration the inflammatory marker the cytokine TNF- α (Tumor Necrosis Factor-alpha) will be performed by means of the enzyme-linked immunosorbent assay (ELISA), following the instructions of the commercial kit.

- 1) Risks and discomforts: Blood collection can generate discomfort at the puncture site (antecubital vein) during the procedure and for a few minutes later. A mild hematoma may occur at the puncture site after the procedure.

MR5® Prototype Device for temporary adjunctive use to relieve pain associated with Lateral Epicondylitis.

- 2) Inclusion and Exclusion Criteria: Subjects with hemophilia or any type of blood clotting disorder, or diagnosed with a chronic immune impairment, will be excluded from the study.

BACKGROUND/RATIONALE: EPICONDYLITIS - TNF- α

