It is known that matrix remodeling is being enabled by the balance of matrix metalloproteinases (MMPs) and their inhibitors. The imbalance in the expression of MMPs and inhibitors can contribute to tendon matrix degradation^{xcix c}. The tendon matrix degradation is initiated by MMPs and involves the release of inflammatory cytokines such as tumor necrosis factor (TNF- α) and interleukins as IL-1, IL-6 and IL-10^{ci}. The presence of these cytokines is directly related to the progression of inflammation and painful processes after tendon disorder^{ci},^{ciii}.

TNF- α is a pleiotropic cytokine related to cell survival and proliferation but also to cell death in the apoptotic process expressed by tenocytes in inflammatory conditions^{civ}. It may be the key cytokine in the origin of several musculoskeletal diseases such as arthritis and tendinitis, the TNF- α expression is increased in tendons with installed inflammatory processes, such as after surgery or injuries^{civ}. The long persistence of inflammation can increase the pro-inflammatory mediators extending the inflammatory phases and favoring the outbreak of scar tissues which alter the characteristics of original tendon^{cvi}. So, in this context, it is important that treatment aims to modulate the inflammation process, promoting a quality tissue repair.

ADVERSE EVENTS EVALUATION: Adverse events evaluation will include, but not be limited to, the following unlikely, but potentially feasible events that may occur from application of the Multi Radiance Medical® MR5® Prototype Device to the treatment site:

- skin irritation
- discoloring
- rash
- indentations
- infection
- increased pain or tenderness

SUBJECT SATISFACTION WITH OVERALL OUTCOME RATING: The subject is asked to indicate how satisfied he or she is with any change in his or her Lateral Epicondylitis pain following completion of the procedure administrations with the MR5®, by responding to the following question by selecting the most appropriate category from the following five-point Likert scale: *“How satisfied or dissatisfied are you with any change you may have noticed in the pain in your neck/shoulder after getting the procedures with the study device?”*

- ✓ Very Satisfied
- ✓ Somewhat Satisfied
- ✓ Neither Satisfied nor Dissatisfied
- ✓ Not Very Satisfied
- ✓ Not at All Satisfied

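### The one named safety test is a conservative corrected chi-square that gives no result at 0 v 0; a risk difference with an exact interval would serve better (minor)

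*Combined protocol and SAP*

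**What the plan says.** The SAFETY ANALYSES section has three sentences. The first sets the population: "Safety analyses will be based on all subjects who were randomized to the test or to the placebo procedure group". The second says safety will be assessed by "evaluating and comparing frequency and incidence of observed and/or reported adverse events" between the groups. The third names the test: "A chi-square test with a continuity correction will be performed to compare the percentage of subjects who had adverse events between test and placebo". No significance level, effect estimate or confidence interval is given for safety.

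Other sections bear on this. ADVERSE EVENTS states: "It is unlikely and not expected that any adverse events will result from implementation of this clinical study protocol". It also has each recorded event "subsequently evaluated by the investigator for its relation to the study procedure", and lists feasible device events: "skin irritation, discoloring, rash, indentations and infection". ADVERSE EVENTS EVALUATION adds "increased pain or tenderness". The TNF-α blood-collection section warns of an event unrelated to the device: "A mild hematoma may occur at the puncture site after the procedure". Both arms have these blood draws. No stated analysis uses the event type or the relation judgement.

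**The concern.** A continuity-corrected chi-square is conservative in small samples, and most so when events are rare. For efficacy, conservatism protects against a false claim. For safety it works the other way, since it makes a report of no significant difference more likely. The results are meant to support a De Novo submission (PROPOSED INDICATIONS FOR USE), so such a report could be read as reassurance.

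If the protocol's expectation is right and nobody has an event, the test yields nothing. The plan then has no statement of which event rates remain possible.

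The any-event endpoint may add to this. A subject already counted for a puncture-site bruise contributes nothing more if a rash appears under the emitter. How much that matters depends on how common unrelated events are.

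**Working it through.** **Inputs.** 30 per arm (Sample size); 25 per arm as an alternative, from the site table in the stratification plan, which totals 50. Two-sided 0.05 is assumed for safety, because the plan states it only for efficacy. The plan gives no safety rate, size or power to reproduce, so all event rates below are assumptions.

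**1. Rejection threshold.** For a v b events with n per arm, N = 2n and m = a + b, the corrected statistic is N(|a(n−b) − b(n−a)| − N/2)² / (n·n·m·(N−m)).
- 5 v 0: 60 × (150 − 30)² / (900 × 5 × 55) = 864,000 / 247,500 = 3.49, p = 0.062.
- 6 v 0: 60 × (180 − 30)² / (900 × 6 × 54) = 1,350,000 / 291,600 = 4.63, p = 0.031.
- 0 v 0: m = 0, so the denominator is zero and there is no result.

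Under the score-based unconditional exact test, 5 v 0 gives p = 0.023.

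**2. True size.** I summed the binomial probabilities of all rejected tables (31 × 31 = 961 at 30 per arm) under a common event rate.

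| Common event rate | 2% | 5% | 10% | 20% | 30% | 50% (maximum) |
|---|---|---|---|---|---|---|
| Size, 30 per arm | 0.00003 | 0.0015 | 0.0094 | 0.022 | 0.026 | 0.0274 |

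The maximum is 0.033 at 25 per arm. At 30 per arm Fisher's test rejects in the same tables and has the same size. The score-based unconditional exact test has maximum size 0.047.

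**3. How likely is 0 v 0?** If each of 60 subjects has a 1% chance of any event, the probability is 0.99^60 = 0.55; at 2% it is 0.98^60 = 0.30. The score-based unconditional exact interval for the risk difference at 0 v 0 is about -12% to 12%.

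**4. Power, counting significant results with more events on active.** Other events are assumed independent of site reactions and equally common in both arms, so the any-event rate is 1 − (1 − background)(1 − site). For example, 20% site and 20% background gives 1 − 0.8 × 0.8 = 36% v 20%.

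Site reactions 20% v 0%:

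| Background | Planned test, any event | Exact test, site events (Boschloo to score) |
|---|---|---|
| 0% | 0.57 | 0.75 to 0.88 |
| 5% | 0.40 | 0.75 to 0.88 |
| 20% | 0.20 | 0.75 to 0.88 |

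Each change separately, at 20% background:

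| Site rates | Planned | Exact (score), any event | Corrected test, site events | Exact, site events |
|---|---|---|---|---|
| 5% v 0% | 0.03 | 0.05 | 0.00 | 0.06 (score) |
| 10% v 0% | 0.06 | 0.10 | 0.07 | 0.18 (Boschloo) to 0.35 (score) |
| 20% v 0% | 0.20 | 0.26 | 0.57 | 0.75 (Boschloo) to 0.88 (score) |
| 25% v 5% | 0.18 | 0.24 | 0.44 | 0.58 (score) |
| 30% v 10% | 0.17 | 0.24 | 0.37 | 0.48 (score) |

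At 10% v 0% neither change alone helps much; only both together do. The gap between the exact methods comes from one table: 4 v 0 gives p = 0.047 by the score method and 0.070 by Boschloo.

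**The case against.** The strongest reply is that safety in a 60-subject study is mainly descriptive. Each event is assessed individually by the investigator, and the sentence on frequency and incidence already permits tables by type and relation. A conservative test is still a valid test, and no success criterion uses it. The documents also expect few events, so frequent skin reactions on top of frequent unrelated events would be a surprise. Since the emitter is held against the skin in both arms, contact reactions on sham are plausible, and the comparisons against 0% are the most favourable ones. Most of this stands, and it sets the weight of the point.

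Four stronger readings are tempting and are not supported:
- **The safety analysis is invalid.** It is not: the test's size stays below the nominal level.
- **Pooling hides device reactions.** That depends on the background rate, which the documents do not give. With no background events, the any-event and site-event endpoints coincide and pooling costs nothing.
- **Replacing the test is enough.** At 10% v 0% with 20% background it moves power only from 0.06 to 0.10.
- **Event type and relation are ignored.** Relation is collected, and tables are allowed. The case report forms (Appendix E) are not in the text available, so nothing can be said about whether type and site are recorded. What is missing is a stated analysis that uses them.

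The reply does not answer the 0 v 0 case, the low size at low event rates, or the absence of any estimate with an interval. None of these depends on an assumed difference between the arms.

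**Conclusion.** The point holds at minor weight. At an assumed two-sided 0.05, the planned test has size at most 0.027 at 30 per arm (0.033 at 25), and about 0.009 and 0.0015 at common event rates of 10% and 5%. It rejects against zero events only from 6 v 0, and it returns nothing at 0 v 0. Fisher's test would not change this at 30 per arm.

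The power gain from a better analysis is conditional on unknown rates. It is large if site reactions reach about 20% on active and are rare on placebo. It is modest and dependent on the exact method at 10%, and negligible at 5%. The firm reason to change is that an interval says which differences remain possible when few or no events occur.

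**What to change.** Keep the all-cause comparison in all randomized subjects. Replace the corrected chi-square with the risk difference and an unconditional exact 95% confidence interval. Name the method (for example, score-based) in advance, because the result at 4 v 0 depends on it, and base the interpretation on the interval.

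Add the same estimate for the five device-site skin reactions listed in ADVERSE EVENTS, in subjects who received at least one procedure. Randomization precedes the stabilization week, so some randomized subjects can leave before any exposure. Leave increased pain or tenderness out of this set and report it separately, since it is also the symptom of the disease. State that events will be tabulated by type and judged relation.

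The cost is a few sentences in the SAP, a few tables, and a check that the case report form records type, site and onset. There are two downsides. It adds one comparison, and blinded judgement is needed to separate bruising from the antecubital draw from discoloring under the emitter. Retaining the all-cause comparison guards against misattribution.
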